suggesting: a) strong initial uptake of e-cigarette, b) favorable liking/satisfaction/withdrawal relief, and c) that these effects are not nicotine specific (few differences between active vs. placebo). We also just completed a R21 that is thematically very similar to the current trial: 68 participants randomized to receive e-cigarettes (again, BluCig) or not, with a naturalistic sampling period and prospective follow-up. The R21 used ecological momentary assessment (EMA) methods to capture uptake patterns among smokers who are provided an e-cigarette. The study included a control group (Total N=68) that allows us to compare prospective changes in smoking behavior as compared to smokers who do not receive an e-cigarette (BluCig). Manuscript is in preparation and results are to be presented at SRNT 2017. Figure 1 shows uptake and amount of usage of e-cigarettes, during and following the sampling period. General uptake during the 3-wk sampling period was strong: 100% of those receiving BluCig used at least once, 71% reported regular use during at least 1 of the 3 sampling weeks, and 63% used daily during at least 1 week. Smokers in the e-cigarette group were 2.9x more likely (41 vs. 14%) to independently purchase their own e-cigarette, 1.6x more likely (44% vs. 27%) to make a quit attempt, and 3x more likely (15% vs. 5%) to achieve “floating abstinence” (any 7-day period of non-smoking, ever within study). Cessation-related outcomes were non-significant for this small study, and we caution against over-interpretation since confidence intervals (not shown here) are wide. We found significant reductions in both CPD and CO/NNAL, but no changes in cotinine. EMA data suggested clear contextual differences for e- vs. conventional cigarettes. EMA compliance was strong: 80% of participants completed at least 12 diaries in 3 weeks (most comparable to herein) and 78% completed at least 3 diaries/week. These early results show: a) general congruence of outcomes to those we hypothesize for the proposed larger trial, b) palatability of product, c) uptake/use even without structured instructions to do so, and d) our strong experience in methods: recruitment, sampling product, EMA, biomarkers, and product evaluation. The general methods and measures from these studies guide our current trial, though we now turn to a 2nd generation device, which should have even fewer barriers to uptake and/or substitution.

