(440 e-cigarette vs. 220 control). With this sample, we have 80% power to detect differences of 10% vs. 18.5%, with a two-sided $\alpha=0.05$ chi-square test. If provision of e-cigarettes should undermine quitting, we are able to detect a decrement of 4% (8% vs. 4%; OR = .48; 95% CI: 0.23 - 0.98).

Precision of Proportional estimates within Aim 1 With 440 e-cigarette participants, a two-sided 95.0% confidence interval will have a maximum half-width of 0.047 (for any outcome in Aim1) (e.g., 95% CI on an observed rate of 50% would range from 0.453 to 0.547). As the observed proportion deviates from 50% (either higher or lower), the 95% confidence interval will decrease in width, providing more precision on the estimate (e.g., 95% CI on 90% would range from 0.872 to 0.928). A confidence interval as wide as +/- 5% is a relatively small width and one we are willing to accept for our estimates on uptake, adoption, and patterns of dual use.

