Hyp 3: Provision and use of e-cigarettes will lead to increased incidence of (Hyp3a) quit attempts, (Hyp 3b) cessation, and (Hyp 3c) motivation/confidence to quit. Logistic regression analyses will be performed with (1) any quit attempt [QA] within 6 months (1=one or more quit attempts, 0=none), (2) any 24hr QA (same), (3) point prevalence abstinence at 6 months (1=7 day abstinence at 6 months, 0=not abstinent), and (4) floating abstinence (1=any 7 day period of abstinence during study, 0=no abstinence) as the outcomes and group (e-cigarette vs. control) as the covariate. The coefficient on group provides a log odds ratio for measuring the odds of (1) any self-defined QA's, (2) 24hr QA's, (3) point prevalence abstinence, and (4) floating abstinence. Statistical significance of these coefficients will be assessed using a p-value with a two-sided $\alpha=0.05$, and both the odds ratio and its 95% confidence interval (CI) will be reported. Motivation and confidence to quit are evaluated on a continuous scale (0-10), and linear regression models will be used for both, with group (e-cigarette vs. control) as the covariate (along with any other baseline differences as covariates). To fully capitalize on the longitudinal nature of our data, secondary analyses will include a) regression analyses where number of QA's are compared across groups using poisson or linear regression (depending on the distribution of QA's), b) latency to any quit attempt, and c) stability of e- and conventional cigarette use over time. We will also repeat above analyses: a) based on those who do vs. do not use e-cigarettes, and b) using quit attempts and abstinence of all tobacco products, including e-cigarettes.

Ancillary Analyses:

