Hyp 3: Provision and use of e-cigarettes will lead to increased incidence of (Hyp3a) quit attempts, (Hyp 3b) cessation, and (Hyp 3c) motivation/confidence to quit. Logistic regression analyses will be performed with (1) any quit attempt within 6 months (1=one or more quit attempts, 0=none), (2) any 24hr quit attempt (1=one or more 24 hour quit attempt, 0=none), (3) point prevalence abstinence at 6 months (1=7 day abstinence at 6 month call, 0=not abstinent), and (4) floating abstinence (1=any 7 day period of abstinence during study, 0=no abstinence) as the outcomes and group (e-cigarette vs. control) as the covariate. The coefficient on group provides a log odds ratio for measuring the increased odds of (1) any self-defined quit attempts, (2) 24hr quit attempts, (3) point prevalence abstinence, and (4) floating abstinence in the e-cigarette group compared to the control group. Statistical significance of these coefficients will be assessed using a p-value with a two-sided alpha of 0.05, and both the odds ratio and its 95% confidence interval (CI) will be reported. Motivation and confidence to quit are evaluated on a continuous scale (0-10), and linear regression models will be used with motivation/confidence to quit at 6 months as the outcomes with group (e-cigarette vs. control) as the covariate (along with baseline motivation/confidence and any other variables that are different between groups at baseline treated as covariates). Secondary analyses will include regression analyses where number of quit attempts are compared across groups using poisson or linear regression (depending on the distribution of number of quit attempts). We will also repeat this analysis: a) based on those who do vs. do not use e-cigarettes, and b) using quit attempts and abstinence of all tobacco products, including e-cigarettes.

10. Quality Assurance Plan

The REDCap system has validation options to not accept outliers, illogical response patterns, etc. The PI will have weekly meetings with the research assistants to discuss qualitative comments received during data collection and any problems in data collection. The statistician will periodically examine the database to look for irregularities. Initial data analyses will examine distributions of variable scores, comparability of baseline characteristics, follow-up rates and use of extra-study cessation treatment across conditions in case analyses need to be adjusted for these.

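### If Poisson regression is chosen for the number of quit attempts, the plan makes no allowance for overdispersion, and it states no criterion for choosing between Poisson and linear regression.

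*Combined protocol and SAP*

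**What the plan says.** Under Statistical Considerations – Data Analyses, Hyp 3, the number of quit attempts is listed among the secondary analyses, to be "are compared across groups using poisson or linear regression" depending on the distribution. The Data and Safety Monitoring Plan, item 9 (Data Analysis Plan), repeats this: "Secondary analyses will include regression analyses where number of quit attempts are compared across groups", by "poisson or linear regression (depending on the distribution of number of quit attempts". Neither place mentions a dispersion check, scaled or robust standard errors, a negative binomial model, or a criterion for the choice.

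The quit-attempt outcomes listed first under Hyp 3 are binary. One is "any quit attempt within 6 months (1=one or more quit attempts, 0=none", and the other is the 24-hour version. Both are analysed by logistic regression at a "two-sided alpha of 0.05".

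Three other statements bear on the count:
- The opening of the Data Analyses section plans exploratory graphs and summaries of every outcome, but to decide whether transformations are needed.
- The same section adds covariates where the groups differ significantly at baseline, and its conservative missing-data rule treats missing outcomes as no quit attempt.
- The only quit-attempt rates given are the pilot's, under Ongoing / Recent studies of e-cigarettes: "1.6x more likely (44% vs. 27%) to make a quit attempt".

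**The concern.** A Poisson model fixes the variance of the count at its mean. If the true variance is larger, model-based standard errors are too small, and a group difference is declared more often than the nominal 5%.

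The design gives a reason to expect this. The eligibility section admits smokers whether or not they want to quit. The Randomization section expects readiness to quit to moderate outcomes and stratifies on it. Readiness is not named as a covariate for the count. It would enter only if the groups happened to differ on it, which stratification makes unlikely. Differences between people in their rate of attempts would therefore stay in the residual variation.

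The choice of model is a separate matter. Poisson regression estimates a rate ratio and linear regression a difference in means, so leaving the choice to the observed distribution leaves the reported effect measure open until the data are seen. The Hyp 3 text also plans to repeat its analyses by e-cigarette use and for all tobacco products, so the same gap could carry over to those.

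**Working it through.** **Inputs from the documents.** Arm sizes "440 e-cigarette vs. 220 control"; two-sided 0.05, stated for the logistic coefficients and assumed here for the count model; pilot shares with any attempt of 44% and 27%. The plan states no mean, variance or power for the count, so there is no figure of its own to reproduce. The variance-to-mean ratio φ is an assumption, taken over a range.

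**Do the pilot shares show overdispersion?** A Poisson count with mean m has P(0) = exp(−m).
- 27% with any attempt: m = −ln(0.73) = 0.315.
- 44% with any attempt: m = −ln(0.56) = 0.58.

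Both shares fit variance equal to mean exactly. They also fit overdispersed counts. For a negative binomial, m = −ln P(0) × (φ − 1)/ln φ:

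| φ | mean if 27% make any attempt | mean if 44% do |
|---|---|---|
| 1 (Poisson) | 0.315 | 0.58 |
| 1.5 | 0.388 | 0.715 |
| 2 | 0.454 | 0.837 |
| 3 | 0.573 | 1.056 |

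Without the mean number of attempts, the pilot cannot tell these rows apart.

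**Why φ above 1 is plausible.** If person i makes Poisson attempts at rate λᵢ, then Var(Y) = E(λ) + Var(λ), which exceeds the mean whenever rates differ between people. The missing-data rule adds a little. With 10% missing set to zero and a Poisson mean of 0.6, φ = 1 + 0.1 × 0.6 = 1.06.

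**Effect on the Poisson test.** The ratio of model-based to true standard error is 1/√φ, so the true two-sided error at nominal 5% is 2(1 − Φ(1.96/√φ)).

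| φ | 1/√φ | true error |
|---|---|---|
| 1 | 1.00 | 5.0% |
| 1.5 | 0.82 | 11.0% |
| 2 | 0.71 | 16.6% |
| 3 | 0.58 | 25.8% |

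In the other direction, suppose nobody makes more than one attempt and 27% make one. Then φ = 1 − 0.27 = 0.73, 1.96/√0.73 = 2.29, and the true error is 2.2%, so the test is conservative.

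**Simulation check.** 10,000 trials per setting, 220 vs 440, no group effect, means 0.315, 0.6, 1.0 and 2.0, φ from 1 to 3 (Poisson at φ = 1, negative binomial above it):
- Poisson with model-based errors: about 5% at φ = 1, 11% at 1.5, 16–17% at 2, 25–26% at 3.
- Poisson with robust errors: 4.8% to 5.8%.
- Linear regression: 4.5% to 5.3%.

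With illustrative means of 0.315 vs 0.58, the linear standard error was about 10% too large, because the larger arm is also the more variable one.

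**The case against.** The strongest reply has four parts.

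First, a reader might infer from the pilot's 56% and 73% with no attempt that the counts have excess zeros. They do not show this: a plain Poisson reproduces both shares. The pilot had 68 participants, and the protocol itself warns that its intervals are wide. Nothing in the documents describes a small group of frequent attempters. This part stands, and the degree of overdispersion remains an assumption.

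Second, a reader might infer that both named models give standard errors that are too small. The linear branch does not. It estimates its own residual variance and held its type I error in simulation. This part stands, and the inflation is confined to the Poisson branch.

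Third, Poisson is not fixed in advance, and the text does not rule out robust errors. That is true, so it would be wrong to say the p-values will be too small. But the qualifier gives no criterion, the exploratory step is directed at transformations, and silence on the error model leaves model-based errors open.

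Fourth, this is a secondary analysis. Overdispersion of a count has no bearing on the binary Hyp 3 tests, and the trial is sized on 6-month abstinence. This part stands in full and makes the point a minor one.

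**Conclusion.** The point holds in conditional form. The plan does not say how overdispersion would be checked or handled if Poisson is chosen, or what would decide between Poisson and linear regression. If Poisson is used with model-based errors and the variance is 1.5 to 3 times the mean, a nominal 5% test has a true error of about 11% to 26%. At a ratio of 1 there is no inflation, and below 1 the test is conservative. The range of ratios is assumed, and the only support for values above 1 is the mix of readiness to quit in the enrolled sample. For the linear branch, the objection is to an effect measure chosen after the data are seen, not to its error rate. The importance is low: one secondary analysis and any repeats of it.

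**What to change.** In both places (Statistical Considerations – Data Analyses, Hyp 3, and Data and Safety Monitoring Plan item 9), replace the choice between Poisson and linear regression with one pre-specified model. Either Poisson regression with robust (sandwich) standard errors or negative binomial regression would do. Report the rate ratio with its 95% CI. The simulation covered the robust-error option, not a fitted negative binomial model. Robust errors also correct the conservative case if counts turn out underdispersed.

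The cost is one sentence in each place. If the counts are overdispersed, the intervals will be wider than the model-based Poisson ones by a factor of √φ: 1.22 at φ = 1.5, 1.41 at 2 and 1.73 at 3. That is the width the data support. At φ = 1 essentially nothing is lost. No change to the sample size or to the logistic analyses is needed.

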Most e-cigarette studies are 1) lab-based measures of pharmacokinetics or toxicant exposure 2) cross-sectional studies of prevalence and predictors of use or 3) uncontrolled cohort studies. The two big remaining questions are uptake among non-smokers (not addressed here), and the impact of e-cigarette use among smokers. This latter question is important to the ongoing public health debate about where these products fit within tobacco control. **E-cigarettes may lower *individual* health risk, but this may or may not translate to reduced population risk.** Four limitations exist within the literature. First, most studies lack a control group and as such they are merely descriptive in nature. Second, when studies do include a comparison group, they are almost invariably based on groups of self-selected users vs. non-users, which are inherently biased and limit ability to draw causal inferences. Third, these studies describe attitudes and patterns of use among established users, but say nothing about uptake, trial, and adoption of e-cigarettes among smokers who newly use these products, assessed concurrent in real time. Fourth, these studies provide minimal data (with appropriate control comparisons) on concurrent and downstream effects on behavior. There is strong need for randomized trials to assess these outcomes. Our **guiding PREMISE** is that **there has yet to be a study that a) randomizes smokers to e-cigarettes vs. not, b) is focused on naturalistic outcomes; i.e., not cessation focused, c) is prospective, with sufficient follow-up duration, d) provides data on nicotine/tobacco exposure, e) is of sufficient sample size, and f) is US-based, an important consideration given upcoming regulation.** We know of no study that meets even two of these criteria.

INNOVATION

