Our study is not purely naturalistic, but it comes close. We provide product for free, mailed directly to participants. This allows us to examine uptake in the absence of cost/access barriers. Asking smokers to pay for e-cigarettes might provide a truly real world test of uptake, but without large numbers of participants, does not allow for assessment of uptake and impact on smoking. We have very little interaction with participants other than through assessments, and never instruct on cigarette or e-cigarette use. We provide referrals to cessation support (quitlines) for those who wish it. This is not a cessation trial, but rather an observational study of smokers over time, some of whom are randomized to receive e-cigarettes to use however they wish, or not at all. Randomization removes self-selection bias that is so common in the existing literature. It also allows for prospective analysis of uptake, use, trial, and adoption among smokers exposed/offered a product, with needed comparison to those who are not given product. Smokers both wanting to quit and not will be enrolled. Our primary focus in this study is the impact of e-cigarette use upon smoking behavior, with emphasis on uptake/usage/adoption, as well changes in smoking. However, with such a large study, among the first of its kind in the U.S., we believe that omission of cessation/quit attempt outcomes in this study would be a significant lost opportunity. Furthermore, if there are group differences in cessation, we believe it would be another lost opportunity to be underpowered to detect them. Thus, our trial is powered on naturalistic rates of point prevalence

abstinence at six-month follow-up, but we again emphasize that we are not promoting or testing e-cigarettes as a cessation intervention.

Regulatory Issues

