Control Group Smokers in this group will smoke their own brand of cigarettes, as they wish, for the duration of the sampling period, but will engage in all study assessments including diary assessments. We considered a placebo-controlled study, but our interest is not in the pharmacological intake of nicotine (vs. not), but rather the use (inclusive of behavioral substitution) vs. non-use of e-cigarettes. Blinding of active vs. placebo e-cigarettes is easily managed for lab-studies, but less so for nationwide, naturalistic studies. To control for cost differential with e-cigarette group, participants in the control group will receive extra reimbursement; we do not want changes in behavior to be a function of free product. We debated whether to provide same general message of e-cigarettes as above. On one hand, doing so would decrease study-induced demand to try e-cigarettes, making this equivalent across groups. However, this would artificially inflate e-cigarette use within the non-sampling control group, which impinges on internal validity. We opt not to include such messaging, but will acknowledge

this as a potential confound. We do anticipate that some control participants will use e-cigarettes, and this too is an outcome we assess (along with all other uptake variables). Within our R21, 1/21 control participants (4.7%) used an e-cigarette (see Figure above). E-cig use is escalating, but still low and we expect nominal initiation within control group. Primary analyses will be based on ITT principles (i.e., group assignment as the independent variable, not product use).

Smokers in both groups will be assessed at screening for interest in cessation support. All comers will be accepted, but smokers actively using cessation medication at baseline will be excluded. At all contacts, we will assess motivation to quit and, as necessary, offer referral information to state quitlines. Such transitions to cessation support are included as study outcomes.

Diary of E-cigarette Uptake

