All analyses are based on an intent-to-treat approach, and are nearly identical to analyses from our prior studies. Exploratory analysis will be performed on all outcomes, and both graphical displays and summary statistics will help determine if transformations will be needed. Any significant baseline differences between groups will be included in regression analyses described below. Missing Data: The most conservative approach for handling missing data (136) is to substitute them with baseline values, assuming outcomes have all returned to baseline, with no quit attempts made. If this assumption is incorrect, it biases the results towards the null by reducing between group differences (136). SRNT recommendations (136) suggest that when there are small amounts of missing data (< 10%) the conservative approach can be used with little bias in outcome. If missing data >10%, we will calculate results not only using this conservative method but also using methods in which missing data are imputed as described in the SRNT guidelines. We will also assess whether dropout is differential by study group. In our current and recent studies of cessation induction, this has not been the case, and we expect similar results here. Finally, though sex/gender is not an explicit focus, we are well poised, given our sample size, to address **potential sex/gender influences** on study outcomes.

Hyp 1a: Within the e-cigarette group, we hypothesize that at least 90% of smokers will try at least once, 45% will use regularly (at least 4/7 days, at any time during follow-up), 25% will use daily for ≥ 7 days (at any time during follow-up), 25%/10% will be using at least some/daily at final follow-up, and 20% will independently purchase e-cigarettes. Within the e-cigarette group (N=440), we will analyze prevalence of each definition of uptake. We will estimate each of these parameters, and the 95% confidence interval for each proportion.

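### The supplementary rerun of Hyp 3 by actual e-cigarette use is a self-selected comparison that can show an effect where none exists; label it associational and base any statement about the effect of use on assignment

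*Combined protocol and SAP*

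**What the plan says.** Under Statistical Considerations – Data Analyses, Hyp 3 is tested by logistic regression for any quit attempt, any 24-hour attempt, 6-month point prevalence abstinence and floating abstinence. Group is the covariate; odds ratios, 95% intervals and a two-sided 0.05 level are specified. Motivation and confidence are analysed by linear regression. The section then adds that these analyses will be repeated "based on those who do vs. do not use e-cigarettes". The Data and Safety Monitoring Plan, section 9, has nearly the same sentence: "We will also repeat this analysis: a) based on those who do vs. do not use e-cigarettes".

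Four other statements bear on this:

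- The Glaring Literature Gap criticises studies that compare "groups of self-selected users vs. non-users, which are inherently biased and limit ability to draw causal inferences".
- The section on whether the study is naturalistic says: "Randomization removes self-selection bias that is so common in the existing literature".
- Control Group says: "Primary analyses will be based on ITT principles (i.e., group assignment as the independent variable, not product use".
- The opening of the Data Analyses section says: "All analyses are based on an intent-to-treat approach".

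For the rerun itself, neither place defines use or says by when it must have occurred. Neither says whether control participants who obtain e-cigarettes count as users. There is no requirement that use precede the outcome, no adjustment specific to this comparison, and no label marking the result as non-causal.

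**The concern.** Whether a participant uses e-cigarettes is decided after randomisation and may track the wish to quit. The protocol gives grounds for expecting this. Randomisation is stratified on desire to quit because readiness may moderate outcomes. The literature section lists quitting and cutting down among common reasons for use. The e-cigarette-arm script mentions both purposes. If motivated smokers both use more and quit more, users will show more quitting even with an inert product.

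Timing adds a second route. Hyp 1a counts regular use at any time during follow-up, so use could follow a quit attempt or form part of it. Without an order rule, the outcome may be driving the exposure.

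At stake is a supplementary odds ratio with a p-value that may disagree with the randomised result through selection alone, in a report that gives the reader no warning.

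**Working it through.** **1. The plan's own sample size.** Inputs from Sample Size & Power: 8% vs 16% abstinence, 2:1 allocation, two-sided 0.05, 80% power. With the pooled-variance two-proportion formula,

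n(control) = [1.96·√(p̄(1−p̄)(1+1/2)) + 0.842·√(0.08·0.92 + 0.16·0.84/2)]² / 0.08², with p̄ = (0.08 + 2·0.16)/3 = 0.133.

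This gives 200.2 controls, or about 600 in total (603 after rounding each arm up), matching the plan's 600. It depends only on the randomised contrast.

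**2. Rerun by use when nothing works.**

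*From the documents:* arms of 440 and 220; 8% abstinence overall; 90% any use or 45% regular use in the e-cigarette arm (Hyp 1a); pilot control use of 1/21, rounded to 5%.

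*Assumed, not in the documents:* 40% of smokers are motivated; they quit at 14% and the rest at 4% (0.40·0.14 + 0.60·0.04 = 0.08); the use gradients are those in the table; control use is 5% in both strata under either definition of use.

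Worked case, regular use of 70% in motivated and 28% in other smokers (0.40·0.70 + 0.60·0.28 = 0.448):

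- Motivated users: 440·0.40·0.70 + 220·0.40·0.05 = 127.6.
- Other users: 440·0.60·0.28 + 220·0.60·0.05 = 80.5. Total users 208.1.
- Non-users: 264 − 127.6 = 136.4 motivated and 396 − 80.5 = 315.5 others. Total 451.9.
- Quit rate in users: (127.6·0.14 + 80.5·0.04)/208.1 = 10.1%.
- Quit rate in non-users: (136.4·0.14 + 315.5·0.04)/451.9 = 7.0%.
- Odds ratio: (0.1013/0.8987)/(0.0702/0.9298) = 1.49.
- Rejection probability: difference 0.0311, pooled SE 0.0227, unpooled SE 0.0241, so 1 − Φ[(1.96·0.0227 − 0.0311)/0.0241] = 29%.

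The same steps for the other cases give:

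| Meaning of use | Use: motivated / other | Odds ratio | False positives |
|---|---|---|---|
| Regular (45%) | 70% / 28% | 1.49 | 29% |
| Regular (45%) | 60% / 35% | 1.27 | 14% |
| Any (90%) | 100% / 83.3% | 1.17 | 7.8% |
| Any (90%) | 98% / 84.7% | 1.13 | 6.7% |
| Any (90%) | 95% / 86.7% | 1.08 | 5.6% |

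Any use does little harm because users (440·0.90 + 220·0.05 = 407) and non-users (253, of whom 209 are controls) nearly reproduce the arms.

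**3. Check with different assumptions.** A simulation of 440 vs 220 under a strict null (40,000 replicates per scenario, Wald test of the log odds ratio) took half the sample as motivated. These were 1.2–3 times as likely to use and 2–4 times as likely to be abstinent (1.5–3 times for a quit attempt).

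- Abstinence, regular use: odds ratio 1.05–1.57, false positives 5.3–33.9%.
- Abstinence, any use (use ratio 1.2): 5.3–7.4%.
- Any quit attempt, at the pilot control rate of 27%: with regular use, 21.8% when both ratios are 2 and 74.3% when both are 3; with any use, 6.4–14.3%.
- By assigned group: 4.4–5.3% in every scenario.

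The use-based test held its level only when use was unrelated to motivation, or motivation to quitting.

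**4. Assignment-based alternative.** Complier-average effect = ITT difference / arm difference in any use. The multiplier is 1/(0.90 − 0.05) = 1.18. The planned 8-point difference becomes 8/0.85 = 9.4 points. When the ITT effect is zero, this estimate is zero too.

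**The case against.** The plan already states which result governs: primary analyses follow assignment, not use. Aim 3 ties its hypothesis on provision and use to the control group, and the Hyp 3 models use randomised group. A supplementary as-treated analysis beside a randomised result differs from the stand-alone cohort studies that the protocol criticises. Desire to quit is measured at baseline and stratified on, significant baseline differences enter the regressions, and motivation is a listed moderator. On the plainest reading, use means any use, and inflation for abstinence is then small.

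Most of this stands, and it limits the point to a supplementary analysis. A reader might infer from the joint mention of provision and use that Hyp 3 will be judged by comparing users with non-users; Aim 3 and the models contradict that. What the objection does not remove is the bias itself. The rule on baseline differences covers only measured imbalances that reach significance, if it applies to user groups at all. The any-use reading is plausible but not stated, and inflation under it remains larger for quit attempts.

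An assignment-based estimate also has limits. It adds little beyond ITT at 90% vs 5% use, and its exclusion assumption is open to doubt.

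**Conclusion.** The point holds for the supplementary rerun only. The plan schedules a self-selected comparison that its rationale rejects and that its blanket intent-to-treat statement excludes. In the cases tabulated, false positives for abstinence are about 6–8% with any use and 14–29% with regular use, against a nominal 5%.

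Those sizes rest on assumed gradients. The documents establish that bias is possible and make its direction plausible, but not its amount, and it would reverse if less motivated smokers used more. A reader might take 29%, or the 74% for quit attempts, as the plan's error rate; the documents supply neither the gradients nor the definition of use that would support this. Nor do they support a claim that the primary cessation result is biased.

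This is a cheap improvement, not a threat to the trial's main inference.

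**What to change.** In Hyp 3 of the Data Analyses section and in section 9 of the monitoring plan:

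1. Label the comparison of users with non-users as associational and not as a test of Hyp 3. Significance tests need not be dropped if the label is clear.
2. Define use (any or regular, and by when), say how control-arm users are classified, and require use to precede the outcome.
3. Adjust for baseline desire to quit, already a stratification factor, and baseline dependence, already measured. This handles measured confounding only.
4. For any statement about the effect of use, report the complier-average estimate: ITT difference divided by the arm difference in any use, with a bootstrap interval.
5. Reword the statement that all analyses are intent-to-treat so that it allows for this labelled exception.

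The cost is SAP wording and one short analysis. The instrument-based interval will be wider than the ITT interval. Its exclusion assumption, that assignment affects quitting only through use, must be stated as strained. Only the e-cigarette arm receives the script mentioning cutting down or quitting, and only controls receive the extra reimbursement.
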